5.4. Immunogenicity

5.4.1. Analysis of immunogenicity planned in the protocol

Not in the scope of this SAP

5.4.2. Additional considerations

Not applicable

5.5. Analysis of safety and reactogenicity

5.5.1. Analysis of safety and reactogenicity planned in the protocol

The primary analysis will be performed on the Solicited Safety and Unsolicited Safety sets.

Table 6 Statistical analysis methods for the primary study objectives

Endpoint	Statistical Analysis Methods
Primary	Within groups assessment
-	The overall incidence, with exact 95% confidence intervals (CIs) of any solicited AE (local or
	general), of at least 1 solicited local AE and of at least 1 solicited general AE during the 7-day
	(Day 1-7) period will be tabulated per study group and for each dose and overall. The same
	calculations will be performed for solicited AEs rated as grade 3 and fever >40°C/104°F.
	The overall incidence, with exact 95% confidence intervals (CIs) of any unsolicited AE,
	unsolicited AEs by MedDRA system organ class and by preferred term during the 30-day (Day
	1-30) follow-up post-vaccination period will be tabulated per study group and after each dose
	and overall. The same calculations will be performed for unsolicited AEs rated as grade 3, for
	unsolicited AEs causally related to vaccination and for grade 3 unsolicited AEs causally related
	to vaccination.
	The number and percentages of subjects who experienced at least one SAE or any pIMD during
	the entire study period (Groups 1-3 Day 1-366, Groups 4 and 5 Day 1-426) will be reported.
	I ne percentage of subjects having naematology and blochemistry results below of above the
	normal laboratory ranges with the changes from the baseline values will be tabulated by time
	point for Group 1 to 4 and Group 5 Step 1.
	Duration will be presented.
	The verbalin reports of unsolicited symptoms will be reviewed by a GSK physician and the
	Tarminology
	Cerieve adverse events and withdrawel due to adverse event(e) will be described in detail
	Serious adverse events and withdrawal due to adverse event(s) will be described in detail.

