#### 208833 (STAPH AUREUS BIOCONJ-001 STG) Protocol Amendment 6 Final

#### JCI

e Visit 2 and 6: Clinical visit for PoP Step 1 subjects (i.e. first 40 subjects enrolled in the PoP) where 6 mL of whole blood for safety laboratory evaluation will be collected; Phone call for PoP Step 2 subjects (i.e. all those following subjects after the first 40 enrolled in the PoP Step 1).

f Remind subjects that the device is now ready to collect after Dose 2 data.

 The blood sampling for safety lab evaluation only (~6 mL to be drawn from PoP Step 1 subject only) should occur on Day 1 and Day 61 but, as an alternative, can be performed up to 1 day before vaccine administration.

hUnscheduled visits can occur at any time after first study vaccination and should happen as soon as possible after signs/symptoms onset

Occurrence of solicited AEs within 30 minutes post vaccination observation must be recorded in the eCRF

a/b = vaccine/placebo

pIMDs = potential Immune-Mediated Diseases SAE = Serious Adverse Event Vac = Vaccination M = Month V = Visit
Whenever possible, the investigator should arrange study visits within the intervals described in Table 5 and Table 6.

| Table 5 | Intervals between study visits (dose-escalation safety lead-in |
|---------|--|
|         | epochs)  |

| Groups     | Interval  | Optimal Length of | Allowed        |
|------------|---|-------------------|----------------|
|            |   | interval          | interval       |
| Group 1a/b | V0-Grp1-3 (Day -1)→ V1-Grp1-3 (Day 1)                     | 1 days            | 0 - 3 days *   |
| Group 2a/b | V1-Grp1-3 (Day 1)→ V2-Grp1-3 (Day 8)                      | 7 days            | 7 - 8 days     |
| Group 3a/b | V1-Grp1-3 (Day 1)→ V3-Grp1-3 (Day 31)                     | 30 days           | 30 - 33 days   |
|            | V1-Grp1-3 (Day 1)→ V4-Grp1-3 (Month 6, Day 181)           | 180 days          | 180 - 190 days |
|            | V1-Grp1-3 (Day 1) $\rightarrow$ V5-Grp1-3 (Month 12, Day  | 365 days          | 365 - 380 days |
|            | 366)  |                   |                |
| Group 4a/b | V0-Grp4 (Day $-1$ ) $\rightarrow$ V1-Grp4 (Day 1)         | 1 days            | 0 - 3 days *   |
|            | V1-Grp4 (Day 1) $\rightarrow$ V2-Grp4 (Day 8)             | 7 days            | 7 - 8 days     |
|            | V1-Grp4 (Day 1)→ V3-Grp4 (Day 31)                         | 30 days           | 30 - 33 days   |

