### • Sampling schedule:

Blood samples for laboratory safety evaluation will be drawn from the first 40 subjects enrolled (i.e. subjects belonging to PoP Step 1)

- Drainage samples will be taken from those subjects performing culture test as study procedures at screening (i.e. Visit 0) and from all subjects with recurrences at the time of recurrence.
- **Data collection:** standardised eCRF. Solicited AEs will be collected using a subject eDiary.
- Safety monitoring:

The enrolment and vaccination in the PoP phase will also follow a staggered approach. After safety assessment (for details refer to Section 8.6.1) of the first vaccination of the first approximately 40 subjects (randomised with a 3:1 ratio either to the GSK *S. aureus* candidate vaccine or to the placebo group) the full enrolment of the remaining subjects in the PoP phase will continue. The remaining subjects will be randomised with a 1:1 ratio either to the GSK *S. aureus* candidate vaccine or to the placebo group).

Safety of the subjects in the PoP vaccination epoch will be monitored for the entire duration of the study with an overall duration of participation for each subject of approximately 14 months (i.e. 12 months after last vaccination).

For both, PoP staggered enrolment/vaccination and the PoP full enrolment/vaccination, the investigator is not permitted to start the administration of Dose 1 for the next group and Dose 2 until receipt of the favorable outcome of the safety evaluation as described in Section 8.6.1.

During the whole study period, if the investigator becomes aware of a holding rule being met, he/she will suspend vaccination and will inform GSK immediately (e.g. in case of death or any life-threatening SAEs).

Refer to Section 8.6 for detailed description of holding rules and safety monitoring. Refer to the iSRC Charter for details about the safety assessment committees evaluation.

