### PoP:

The target enrolment of subjects is event driven (

approach:

- The first approximately 40 subjects will be randomised with a 3:1 ratio (30 subjects receiving GSK *S. aureus* candidate vaccine and 10 receiving placebo).
- The remaining subjects in the PoP epochs will be enrolled approximately 8 days after the last of the approximately 40 subjects was vaccinated (for safety evaluation and consequence on study progress refer to Section 8.6.1). The subjects will be randomised with a 1:1 ratio either to receive the GSK *S. aureus* candidate vaccine or placebo until **CO** (event driven design). It is estimated that a total of approximately 500 to 600 subjects will be vaccinated in the PoP but enrolment may continue until 27 events is reached (see Section 10.1.2).

Allocation of the subject to a treatment number at the investigator site will be performed using a randomisation system on internet (SBIR). The randomisation algorithm will use a minimisation procedure (PoP only) accounting for site and for previous SSTIs yes or no within the last 12 months. Minimisation factors will have equal weight in the minimisation algorithm.

After obtaining the signed and dated ICF from the subject and having checked the eligibility of the subject, the site staff in charge of the vaccine administration will access SBIR. Upon providing the subject identification number, the randomisation system will determine the study group and will provide the treatment number to be used for the first dose.

The number of each administered treatment must be recorded in the eCRF on the Vaccine Administration screen.

When SBIR is not available, please refer to the SBIR user guide or the Study Procedures Manual (SPM) for specific instructions.

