The tests detailed in Appendix 2, Section 12.2 will be performed by the local laboratory at the investigator's site. Results of tests will be needed before vaccination i.e. on the same of the blood draw day for PoP Step 1 or latest on the next day for dose-escalation safety lead-in (see also Section 6.2 exclusion criteria).

- The investigator must review the laboratory report, document this review, and record any clinically relevant changes occurring during the study in the AE section of the eCRF. The laboratory reports must be filed with the source documents. Clinically significant abnormal laboratory findings are those which are not associated with an underlying disease, unless judged by the investigator to be more severe than expected for the subject's condition.
- All laboratory tests with values considered clinically significant abnormal during participation in the study or within 8 days after the last dose of study treatment should be repeated until the values return to normal or baseline or are no longer considered significantly abnormal by the investigator or medical monitor. Refer to

the Section 12.5.6 for clinical laboratory abnormal assessments qualified as AEs or SAEs.

• If such values do not return to normal/baseline within a period of time judged reasonable by the investigator, the etiology should be identified and the sponsor notified.

All protocol-required laboratory safety assessments, as defined in Section 12.2 (Appendix 2), must be conducted in accordance with the SPM and the SoA.

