# Staggered enrolment in PoP epochs (for details see Section 5.2 and Figure 6 and Figure 8):

In a first step (PoP step 1) first dose of vaccination will be performed with a staggered approach. Enrolment will be stopped as soon as 40 subjects have been vaccinated with the first dose of the GSK *S. aureus* candidate vaccine or placebo. Only subjects who already signed the ICF and entered the screening phase, at the time of enrolment hold, will be allowed to continue the study; therefore, approximately 40 subjects (30 subjects receiving GSK *S. aureus* candidate vaccine and 10 receiving placebo) will be evaluated for safety. After iSRC evaluation of unblinded safety data collected up to the Day 8 after first dose (including laboratory assessments) for the last vaccinated subject of this staggered subset (step 1) has shown lack of safety issues, the PoP step 2, (full enrolment of the remaining subjects in the PoP epochs) will continue.

The investigator will not be permitted to start the administration of the second vaccine/placebo dose in the staggered PoP subset from step 1 (approximately 40 subjects) until receipt of the favourable outcome of the SRT and iSRC Chair, which needs to evaluate all the safety data available up to Day 68 (including laboratory assessments) related to the subjects of the fourth group (Full dose adjuvanted) of the last dose-escalation safety lead-in step. Conditionally, unblinded data may be evaluated by iSRC and, only after positive opinion of iSRC, the next step (i.e. second dose of staggered PoP subset) can be started.

All subjects will be closely observed at the site for a minimum of 60 minutes after vaccination. Occurrence of solicited AEs within 30 minutes post vaccination observation must be recorded in the CRF (Table 4).

For both, the dose-escalation safety lead-in and PoP, the investigator is not permitted to start the administration of Dose 1 for the next group until receipt of the favourable outcome of the safety assessment committees evaluation (SRT/iSRC), documented and provided in writing (scanned and emailed), authorising the investigator to proceed (Figure 7 and Figure 8). The same applies for the administration of Dose 2 in the fourth group of the dose-escalation safety lead-in and for the administration of Dose 2 in the staggered enrolment of first 40 subjects of the PoP epoch.

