The enrolment and vaccination in the PoP phase will also follow a staggered approach. After safety assessment of the first vaccination of the first approximately 40 subjects (randomised with a 3:1 ratio either to the GSK *S. aureus* candidate vaccine or to the placebo group) the full enrolment of the remaining subjects in the PoP phase will continue. The remaining subjects will be randomised with a 1:1 ratio either to the GSK *S. aureus* candidate vaccine or to the glacebo group.

Safety of the subjects in the PoP vaccination epoch will be monitored for the entire duration of the study with an overall duration of participation for each subject of approximately 14 months (i.e. 12 months after last vaccination).

For both, PoP staggered enrolment/vaccination and the PoP full enrolment/vaccination, the investigator is not permitted to start the administration of Dose 1 for the next group and Dose 2 until receipt of the favourable outcome of the safety evaluation.

During the whole study period, if the investigator becomes aware of a holding rule being met, he/she will suspend vaccination and will inform GSK immediately (e.g. in case of death or any life-threatening SAEs). Please, refer to section 8.6 of the study protocol for detailed description of holding rules and safety monitoring.

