10.1.5.2. Standardized asymptotic confidence intervals around differences in proportions

The standardized asymptotic confidence intervals around differences in proportions are derived using the method of Miettinen and Nurminen [Miettinen, 1985].

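### Pooling PoP unsolicited AEs over Step 1 (3:1, safety bloods) and Step 2 (1:1, no safety bloods) gives an expected vaccine:placebo ratio of about 2.8, with no vaccine effect, for AEs detected only on the Step 1 bloods

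*SAP*

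**What the plan says.** **Allocation by step.** Protocol 7.2.2.1.1 states that the "first approximately 40 subjects will be randomised with a 3:1 ratio", and Protocol 8.6.1 gives the resulting split as "approximately 40 subjects (30 subjects receiving GSK" candidate vaccine and 10 receiving placebo. For Step 2, Protocol 5.2.2 says "The remaining subjects will be randomised with a 1:1 ratio either to the GSK" candidate vaccine or to placebo. SAP 3 repeats both ratios.

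**Laboratory monitoring by step.** Protocol 8.5.7 and Table 25 limit PoP haematology and chemistry to Step 1, on Days 1, 8, 61 and 68. In Step 2 the Day 8 and Day 68 contacts carry no blood draw; Protocol Table 4, footnote e, has "Phone call for PoP Step 2 subjects (i.e. all those following subjects after the first 40 enrolled in the PoP Step 1").

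**From laboratory finding to AE.** Protocol 8.5.7 requires the investigator to "record any clinically relevant changes occurring during the study in the AE section of the eCRF". Protocol 12.5.6 makes findings judged clinically significant AEs or SAEs when they meet the definition. Protocol 12.5.2 lists Grade 4 laboratory abnormalities among the SAE criteria.

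**Tabulation.** SAP Table 6 has unsolicited AEs in the 30-day "follow-up post-vaccination period will be tabulated per study group and after each dose" and overall, including by system organ class and preferred term, grade 3 and related. SAP 5.5.2.2 gives the detailed list, again by group. The restriction to Step 1 appears only for the laboratory values: the Laboratory Safety Set (SAP 4.2.5.2) and the out-of-range and toxicity-grade tables (SAP 5.5.1 and 5.5.2.4).

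**The concern.** Step determines both the chance of being on vaccine and the chance that a silent laboratory abnormality is found. When the steps are added together within each arm, a larger share of the vaccine arm than of the placebo arm has been bled. Laboratory-type AEs will then tend to look more frequent on vaccine even if the vaccine does nothing.

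Safety is the primary objective of this first-in-human trial, and preferred-term tables are where a reader looks for sparse signals. The artefact runs in one direction, against the vaccine, and the exact within-group confidence intervals do not reveal it. The SAP recognises that laboratory values exist only for Step 1, but does not carry this over to the AE tables that receive the same findings.

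**Working it through.** **Inputs.** Step 1: about 40 subjects, 3:1 (Protocol 7.2.2.1.1). Step 2: 1:1 (Protocol 5.2.2). Total vaccinated in the PoP: about 500 to 600 (Protocol 5.3). AE rate in bled subjects: not given in the documents, so assumed.

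**The plan's own figure.** 40 × 3/4 = 30 and 40 × 1/4 = 10, which matches the stated 30 and 10.

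**Timing.** The unsolicited AE windows are Days 1–30 and 61–90 (Protocol 12.5.8.1). The post-dose bloods on Days 8 and 68 fall inside them, so their findings reach the 30-day tables.

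**Share of each arm that is bled.** Step 2 per arm = (N − 40)/2.

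| N | Group 5a | Group 5b | Bled, 5a | Bled, 5b | Ratio |
|---|---|---|---|---|---|
| 500 | 30 + 230 = 260 | 10 + 230 = 240 | 30/260 = 11.54% | 10/240 = 4.17% | 2.77 |
| 600 | 30 + 280 = 310 | 10 + 280 = 290 | 30/310 = 9.68% | 10/290 = 3.45% | 2.81 |

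If a share q of bled subjects has an AE found only on those bloods, the pooled rates are q times these shares. The q cancels in the ratio, so 2.77 to 2.81 holds for any q. If the arms ended equal at 250 each, as in Protocol Table 11, the ratio would be (30/250)/(10/250) = 3.0. If Step 1 grew to 60 bled subjects at 3:1 (an assumption), it would be 2.66 at N = 500 and 2.71 at N = 600.

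**Absolute size at an assumed q = 10%.** Expected subjects: 30 × 0.10 = 3 on vaccine, 10 × 0.10 = 1 on placebo.
- N = 500: 3/260 = 1.15% against 1/240 = 0.42%, a gap of 0.74 points.
- N = 600: 3/310 = 0.97% against 1/290 = 0.34%, a gap of 0.62 points.

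At assumed rates of 5% and 20%, the expected counts are 1.5 against 0.5 and 6 against 2.

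**If routine care also finds such AEs in Step 2 (assumed 1%, with 10% in Step 1).**
- N = 500: (3 + 2.3)/260 = 2.04% against (1 + 2.3)/240 = 1.38%, ratio 1.48.
- N = 600: (3 + 2.8)/310 = 1.87% against (1 + 2.8)/290 = 1.31%, ratio 1.43.

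**Any unsolicited AE.** With an assumed background of 20% to 30% in every subject and an independent 5% to 20% laboratory component in Step 1, the pooled ratio at N = 500 runs only from about 1.01 to 1.06. For example, with background 20% and laboratory 10%, the Step 1 rate is 1 − 0.8 × 0.9 = 28%. Then (30 × 0.28 + 230 × 0.20)/260 = 20.92% against (10 × 0.28 + 230 × 0.20)/240 = 20.33%, ratio 1.03.

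**By step.** Within Step 1 the expected rates at q = 10% are 3/30 and 1/10, both 10%, ratio 1.0. Step 2 contributes no blood-detected AEs to either arm. The artefact disappears.

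**The case against.** **Observed counts will be erratic.** With 10 placebo subjects bled, the chance of no such AE on placebo is 0.9^10 = 35% at an assumed 10% rate and 0.95^10 = 60% at 5%. This stands: 2.8 is an expected ratio, not a forecast of the printed table. The rate itself may be low, since a finding must be judged clinically significant and subjects with clinically significant abnormalities at vaccination are excluded (Protocol 6.2.1.2).

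**A reader might infer that grade 3, related or total AEs will be inflated 2.8-fold.** The documents do not support that. Those categories contain all clinical events as well, and move only through their laboratory-detected part.

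**A reader might also infer that clinic visits in Step 1 against phone calls in Step 2 create a further gap.** That is not shown. Step 2 subjects have scripted calls on Days 8 and 68 (Protocol 12.5.8). Protocol Table 4 has all PoP subjects seen on Days 15 and 75, with unsolicited AEs recorded at every contact from Visit 1 to Visit 8. The bloods are the documented difference.

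**The laboratory question is answered elsewhere.** The Step 1 laboratory tables are unaffected, and the internal safety committee reviews unblinded Step 1 data before Step 2 opens. Both points are true, but neither corrects the preferred-term AE tables.

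**Safety is descriptive and within-group.** No error rate is at stake. The Miettinen–Nurminen interval in SAP 10.1.5.2 belongs to an annex of the sponsor's standard rules, so it does not show that a safety difference was planned and dropped. Still, SAP 6 says comparative analyses are meant to characterise the difference between groups, and readers will set Group 5a beside its placebo control.

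**By-step tables may exist in the separate table list (SAP 10.2).** This cannot be checked here. The SAP text does not ask for them.

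**Conclusion.** The point holds for AEs detected only through the Step 1 protocol bloods. With no vaccine effect, the pooled tables carry an expected vaccine:placebo ratio of about 2.8 for such AEs (2.77 at 500 subjects, 2.81 at 600). This rests on a 30:10 split in Step 1, 1:1 in Step 2, and no detection of such AEs in Step 2. At an assumed 1% detection in Step 2 against 10% in Step 1, the ratio falls to about 1.4 to 1.5.

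The absolute effect is small and confined mainly to laboratory-type preferred terms. The SAE table can be touched because Grade 4 laboratory abnormalities count as SAEs. The any-AE rate is essentially unchanged and the laboratory-value tables are sound. This is a predictable display artefact in the primary safety tables that is cheap to remove; it does not undermine the safety analysis as a whole.

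**What to change.** In SAP 5.5.1 and 5.5.2.2:

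1. Add a display of Group 5 unsolicited AEs by step (Step 1, Step 2), by system organ class and preferred term, including grade 3 and related AEs, and the same for SAEs.
2. Footnote the pooled Group 5 tables: laboratory-type terms were ascertained by protocol bloods in Step 1 only, and the arms should be compared on them within Step 1.
3. If a 5a minus 5b difference is reported, stratify it by step. With Mantel–Haenszel weights at N = 600, Step 1 carries 30 × 10/40 = 7.5 and Step 2 carries 280 × 280/560 = 140, so Step 1 has about 5% of the weight (7.5/147.5). The stratified figure therefore mostly describes Step 2, and laboratory terms should be read from the Step 1 table.
4. Keep all AEs in the pooled tables. Removing blood-detected AEs would take genuine events out of the primary safety display, and would need a record of how each AE was detected, which the passages on AE recording do not describe.

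The cost is a few extra tables and a footnote, using data already planned. The downside is that the Step 1 table is small, 30 against 10.

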5.5.2. Additional considerations

5.5.2.1. Analysis of solicited AEs

The analysis of solicited AEs will be performed on the Solicited safety set and Solicited safety set 30 m.

The following local AEs will be solicited for 7 days after each vaccination:

208833 (STAPH AUREUS BIOCONJ-001 STG)

Statistical Analysis Plan Amendment 5

Local AE	Grading	Collection period
Pain at injection site	0: None	Day 1-Day 7
	1: Mild	Day 61-Day 67
	2: Moderate	
	3: Severe	
Redness at injection site	0: < 25 mm diameter	Day 1-Day 7
	1: \geq 25 mm to \leq 50 mm diameter	Day 61-Day 67
	2: > 50 mm to \leq 100 mm diameter	
	3: > 100 mm diameter	
Swelling at injection site	0: < 25 mm diameter	Day 1-Day 7
	1: \geq 25 mm to \leq 50 mm diameter	Day 61-Day 67
	2: > 50 mm to \leq 100 mm diameter	
	3: > 100 mm diameter	

Table 7Solicited local adverse events and their grading:

For the grading definition of Pain please refer to Table 34 of the study protocol.

The percentage of subjects with at least one local solicited AE reported in e-diary, within 7 days period after each dose, will be tabulated by group together with the exact 95% CI [Clopper, 1934]. Similarly, the percentage of doses followed by at least one local solicited AE will be tabulated together with the exact 95% CIs within each group. The same tabulation will be done for grade 3 solicited local AEs.

The following general AEs will be solicited for 7 days after each vaccination:

Table 8 Solicited general adverse events and their grading:

General AE	Grading	Collection period
Headache	0: None 1: Mild 2: Moderate 3: Severe	Day 1-Day 7 Day 61-Day 67
Fatigue	0: None 1: Mild 2: Moderate 3: Severe	Day 1-Day 7 Day 61-Day 67
Nausea	0: None 1: Mild 2: Moderate 3: Severe	Day 1-Day 7 Day 61-Day 67
Vomiting	0: None 1: Mild 2: Moderate 3: Severe	Day 1-Day 7 Day 61-Day 67
Diarrhoea	0: None 1: Mild 2: Moderate 3: Severe	Day 1-Day 7 Day 61-Day 67
Abdominal pain	0: None 1: Mild 2: Moderate 3: Severe	Day 1-Day 7 Day 61-Day 67

208833 (STAPH AUREUS BIOCONJ-001 STG) Statistical Analysis Plan Amendment 5

General AE	Grading	Collection period
Myalgia*	0: None 1: Mild 2: Moderate 3: Severe	Day 1-Day 7 Day 61-Day 67
Shivering*	0: None 1: Mild 2: Moderate 3: Severe	Day 1-Day 7 Day 61-Day 67
Fever	0: < 38°C 1: 38°C to <39°C 2: ≥ 39.0°C to ≤40°C 3: > 40.0°C	Day 1-Day 7 Day 61-Day 67

*This AE will be collected as solicited during the PoP epoch (only for group 5)

For the grading definition of general solicited AEs please refer to Table 34 of the study protocol.

The percentage of subjects with at least one general solicited AE reported in e-diary within 7 days, after each dose will be tabulated by group together with the exact 95% CI.

Similarly, the percentage of doses followed by at least one general solicited AE will be tabulated together with the exact 95% CIs within each group.

The same tabulation will be done for grade 3 solicited general AEs.

The percentages of subjects reporting each individual local and general solicited AE by maximum grading during the solicited follow-up period (i.e., day of vaccination and six subsequent days after each vaccination) will be tabulated with exact 95% CIs after each dose and overall by group. The percentages of doses followed by each individual solicited local and general AE by maximum grading will be tabulated overall by group with exact 95% CIs [Clopper, 1934].

For solicited symptoms, missing or unevaluable measurements will not be replaced. Therefore, the analysis of the solicited symptoms will include only subjects/doses with documented safety data (i.e., symptom screen/sheet completed).

